10. STATISTICAL CONSIDERATIONS

10.1. Patient classification and definition

Treated Patient: Patient who received at least one dose of study drug.

10.2. Analyses, populations, definitions

The analysis of the data on the efficacy will be conducted on the basis of the results of the changes in the intensity of symptoms associated with the respiratory system, the overall wellbeing and the duration of the infection in Patients who participated in all of the assessments outlined in the Study Protocol.

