STATISTICAL METHODS:	The sample size of 500 Patients was based on the feasibility study. The analysis of the data obtained in the Study will be descriptive: the compiled data will consist of summarizing statistics such as quantities, average values, standard deviations, medians, minimal and maximal values of the observed frequencies/proportions. The effectiveness analysis will be conducted on the basis of the population of Patients who will partake in all of the visits described in the Study Protocol.	

Table of contents

Study number: EUP/HED/008/2016 VERSION DATE: 21.11.2016

1. INT	RODUCTION	6
1.1.	Basic information on the subject affliction of this Study	6
1.2.	Information on the study drug	7
1.3.	The clinical reason for conducting this Observational Study	8
2. TH	E AIM OF THE STUDY	9
2.1.	The main aim of the Study	9
2.2.	The additional aim of the Study	9
3. STU	JDY DESIGN	10
3.1.	Basic information	10
3.1.	1. Characteristics of the study population	10
3.1.2	2. Study design	10
3.2.	Endpoints	10
3.3.	Substantiation of the study construction	10
3.4.	Duration of the Study	11
4. CO	MPLIANCE WITH TERMS OF GOOD CLINICAL PRACTICE, ETHICAL ISSUES.	11
5. STU	JDY POPULATION	11
5.1.	Records of the Study participants	11
5.2.	Inclusion criteria	12
5.3.	Exclusion criteria	12
5.4.	Procedures for treatment discontinuation or if the patient withdraws from the study	12
6. ME	THODOLOGY	12
6.1.	Schedule of the Study	12
6.2.	Assessments in a specialist and primary care clinics under the study	13
6.2.	1. Initial visit (Visit 1) - (day 0)	13
6.2.2		•
	the clinical needs of the Patient	
	SESSMENTS PERFORMED IN THE STUDY	
7.1.	Endpoints and the methods of their evaluation	
7.1. ⁻		
	JDY DRUG	
8.1.	Administration of the drug	
8.2.	Patient identification	
8.3.	Drug delivery	
8.4. 9. REI	Concomitant medication PORTING RELATED ADVERSE EFFECTS	
	TATISTICAL CONSIDERATIONS	
10. 5		
IU.I.	F QUEIL GIQSSIIIGAUUT ATU UEIITIUUT	10

DOCUMENT

STATUS: CONFIDENTIAL

10.2	2.	Analyses, populations, definitions	16
10.3	3.	Method of determining the sample size	17
10.4	1.	Statistical analysis	17
1	0.4.1	. Demographic data and other basic characteristics	17
1	0.4.2	2. Distribution of patients and cases of exclusion from the study	17
1	0.4.3	3. Adverse effects analysis	17
10.5	5.	Factors which may affect the statistical analysis and modify the results of the Study	18
10.6	6.	Factors limiting the Study	18
11.	M	ONITORING PROCEDURES	18
12.	MA	ANAGEMENT OF THE STUDY	18

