3.2. Endpoints

The gathering of information on the therapeutic effects of the treatment with the **HEDUSSIN®** medicinal product includes the assessment of: the number of days until full recovery of the Patient measured from the day of the 1st visit until the closure of the observation – the day of the 2nd visit.

- Exclusion from the Study the number of days measured from the day of the 1st visit until the occurrence of complications, intensification of the state, occurrence of additional infections, etc.

 visit 2: closure of the observation and the conducting of a medical interview on the health status/Patient wellbeing.
- The change in the intensity of the symptoms, associated with the respiratory system, resulting
 from the treatment will be assessed on the basis of the BSS scale (Bronchitis Severity Scale)
 (evaluation of the measurements taken during visit 1 and 2)
- The evaluation of the changes in the overall wellbeing resulting from the treatment will be based on the VAS scale (Visual Analog Scale) (evaluation of the measurements taken during visit 1 and 2)
- The evaluation of the treatment tolerance based on the occurrence of sleep quality disturbances and weakness feeling will take place on the basis of a 5-level estimation scale (evaluation of the measurements taken during visit 1 and 2)

All adverse effects caused by the drug must be reported to **Phytopharm Klęka S.A.** or the URPL or to the Study Organizer via the **www.dzialanianiepozadane.com** website.

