5.4. Procedures for treatment discontinuation or if the patient withdraws from the study

If the patient is excluded from the Study (i.e. they discontinue the participation in the Study before the evaluations schedule in the Assessment Protocol), the main reason for discontinuation will be recorded in the Study Questionnaire (SQ). Discontinuation from the study due to adverse effects must be adequately described in the patient records.

The investigator provides patients excluded from the study with adequate further treatment - personally or by another doctor with the existing documentation of the disease course.

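### Efficacy is reported only in children who complete both visits, so a child excluded for worsening, complications or a new infection without a full Visit 2 drops out of the result

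*Protocol*

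**What the plan says.** Two places in the protocol fix the efficacy population. Section 10.2 limits the three efficacy results (respiratory symptoms, wellbeing, infection duration) to results "in Patients who participated in all of the assessments outlined in the Study Protocol". The Statistical Methods entry of the Protocol Summary bases effectiveness "on the basis of the population of Patients who will partake in all of the visits described in the Study Protocol". I read these as the same set, since the schedule in Section 6.1 has only two visits.

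Three other sections bear on who can be in that set:

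- Section 3.2 (Endpoints) contains the item "Exclusion from the Study the number of days measured from the day of the 1st visit until the occurrence of complications, intensification of the state", which goes on to additional infections. It is followed directly by "visit 2: closure of the observation and the conducting of a medical interview on the health status/Patient wellbeing".
- Section 5.4 explains exclusion from the study with the words "they discontinue the participation in the Study before the evaluations schedule in the Assessment Protocol". The main reason is to be recorded in the Study Questionnaire.
- Section 10.1 defines "Treated Patient: Patient who received at least one dose of study drug", but no efficacy analysis is assigned to that group.

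Section 10.4.2 tabulates the numbers treated, discontinued and attending, together with the reasons for discontinuation. Section 10.5 lists missed control visits and unknown fate among the factors that may change the results, and gives no way of handling them.

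**The concern.** Membership of the efficacy set can depend on the outcome. Complications, worsening and new infections are clinical failures of the episode under treatment. If such a child is excluded and has no full Visit 2, the unfavourable course enters none of the three efficacy results named in Section 10.2.

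Nothing in the design offsets this. Section 3.1.2 describes an open-label, non-randomized study and no comparator arm, so the before-after result in the selected children is the whole efficacy statement. Sections 1.3 and 3.3 say that the data will serve marketing campaigns and training, where a recovery or improvement figure will be read as applying to treated children in general.

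This is not a matter left open for a statistical analysis plan. The protocol states the population itself, twice, and a plan that followed it would carry the selection forward.

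**Working it through.** **Inputs.** Planned size: 50 physicians × 10 children = 500 (Section 5.1), which reproduces the 500 of Section 10.3. (Section 5.1 also mentions 3000, which 50 × 10 does not give. That is a separate discrepancy, and nothing here depends on it.) The protocol gives no exclusion rate and no expected response, so every rate below is an assumption shown over a range.

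**Step 1: what follows from the text.** Efficacy requires both visits (10.2, summary). Excluded means gone before the planned evaluations (5.4). Exclusion is linked with complications, worsening or additional infection (3.2). A child excluded for one of these reasons without full Visit 2 assessments is therefore outside the efficacy set. A child who worsens and does have them is inside it.

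**Step 2: proportion improved.** Let r be the proportion improved among completers and f the share of treated children excluded as failures, with no other losses. Counting those children as failures,

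all-treated proportion = r × (1 − f), overstatement = r × f.

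Example: r = 90%, f = 10% gives 0.90 × 450/500 = 81.0%, an overstatement of 9.0 points.

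| f | Children left of 500 | All-treated if r = 80% | Overstatement (points) | All-treated if r = 90% | Overstatement (points) |
|---|---|---|---|---|---|
| 2% | 490 | 78.4% | 1.6 | 88.2% | 1.8 |
| 5% | 475 | 76.0% | 4.0 | 85.5% | 4.5 |
| 10% | 450 | 72.0% | 8.0 | 81.0% | 9.0 |
| 20% | 400 | 64.0% | 16.0 | 72.0% | 18.0 |

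**Step 3: mean symptom change.** Assume that the five items scored 0 to 4 are summed (range 0 to 5 × 4 = 20), that completers change by −5 on average, and that excluded children change by w. The all-treated mean is (1 − f) × (−5) + f × w.

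- w = 0: −4.90 at f = 2%, −4.50 at 10%, −4.00 at 20%.
- w = +2: −4.86 at f = 2%, −4.30 at 10%, −3.60 at 20%.

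The completer analysis would report −5 in every case.

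**Step 4: children whose fate is unknown.** If a share u misses Visit 2 for unknown reasons and a proportion q of them improved, the all-treated proportion is (1 − u) × r + u × q. With r = 80% and u = 10% it lies between 0.9 × 0.80 = 72.0% (q = 0) and 0.9 × 0.80 + 0.1 = 82.0% (q = 1). The completer figure could be 8 points too high or 2 points too low. For this group the sign is not known.

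**The case against.** The strongest reply is that Section 3.2 is a list of endpoints, not a withdrawal rule. The item measures days to an event, and the mention of Visit 2 closing the observation can be read to mean that such a child is still seen. Section 5.3 lists entry criteria only, and Section 5.4 names no clinical trigger. This stands. A reader might infer that the protocol requires every worsening child to be withdrawn, so that all treatment failures leave the result. The documents do not support that. They also do not say that an excluded child receives the full Visit 2 assessments, and the wording of 5.4 points the other way.

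A second reply is that the direction of bias is uncertain. The summary and Section 6.2.2 tie visits to the child's clinical needs, so a recovered child may be the one who does not return. This stands for absence without a known reason (Step 4). It does not apply to children whose recorded reason is worsening, complication or new infection.

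A third reply is that failures are visible elsewhere: discontinuation reasons are tabulated (10.4.2) and days to exclusion are listed in 3.2. That is true, but Section 10.2 carries neither into the efficacy results.

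Finally, the study is uncontrolled and mainly descriptive, so the population is only one of its limits. That is fair, but a descriptive figure should still describe the children who were treated, and Section 10.4 also plans tests of change.

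**Conclusion.** The point holds in this qualified form. The stated efficacy population drops any child excluded for worsening, complications or additional infection who lacks full Visit 2 assessments, and for these children the error favours the product.

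The size cannot be derived from the protocol. With 80-90% of completers improved and 2-20% of treated children excluded as failures, the overstatement runs from 1.6 to 18.0 points. At the low end it is minor. The range assumes that every excluded child is a failure and that there are no other losses.

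A reader might go further and conclude that the both-visits restriction as a whole must flatter the product. That does not follow, because losses for unknown reasons could move the figure either way.

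**What to change.** 1. Reconcile Sections 3.2 and 5.4, so that it is clear whether a child excluded for complications, worsening or additional infection has the Visit 2 assessments.
2. In Section 10.2 and the summary, make the Treated Patients of Section 10.1 the main population for recovery and infection duration. Count a child whose recorded exclusion reason is worsening, complication or additional infection as not recovered, with the infection not ended at exclusion. Ordinary censoring at that day would not be enough, because it assumes that the child goes on to recover like those who stay. State in one line what counts as recovered by Visit 2.
3. For children with unknown fate, keep them in the denominator and show best-case and worst-case recovery.
4. For symptom and wellbeing change, use Visit 2 or closing scores where they exist. Where they do not, show a range under stated assumptions. Sections 5.4 and 6.1 provide for the reason at exclusion but not for scores, so scores at exclusion cannot be taken for granted.
5. Report the both-visits set as supportive.

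The recovery part uses the exclusion reason that is already collected. The cost is revised wording, a little more analysis and possibly less favourable figures.

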5.2. Inclusion criteria

Study number: EUP/HED/008/2016

VERSION DATE: 21.11.2016

Each study participant must meet the following criteria:

- Patient of either sex, aged 2 to 12
- Diagnosis of a productive (wet) cough of various aetiology

The inclusion into the Study will take place during the 1st visit. Only Patients in which the earlier recommendation to use HEDUSSIN® in the therapy of productive cough of various aetiology was made due to solely medical reasons and independently from this Study, and who did not take the first dose of the syrup at the moment of the inclusion, are eligible. The inclusion of the patient into the group where the given treatment method is used should not result from the study protocol. It should be dependent solely on the current medical practice and remain in accordance with the current medical knowledge.

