6. METHODOLOGY

6.1. Schedule of the Study

A summary of observations and assessments that will be conducted during the study is presented in the following table.

Table1. Schedule of the assessments during the Study realisation

PROTOCOL FOR A NON-

INTERVENTIONAL

STUDY

Procedures for particular assessments	Visit 1*	Visit 2*
Demographic data	Х	
Qualification of the Patient into the PAES Study (inclusion criteria)	Х	
History concerning comorbidities and their treatments	Х	Х
Basic diagnosis and its duration	Х	
The dose of the medicinal product used		Х
The assessment of :		
 The symptoms associated with the respiratory system (BSS scale) 		
Assessment of the body temperature	Χ	Х
Assessment of the overall wellbeing (VAS scale)		
Assessment of the sleep quality disturbances		
The use of concomitant treatment		
Duration of the infection (number of days)		Х
Reporting adverse effects related to the HEDUSSIN ® medicinal product use		Х

^{*}The assessments will take place as part of the routine Patient observation

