8. STUDY DRUG

8.1. Administration of the drug

PROTOCOL FOR A NON-

INTERVENTIONAL

STUDY

The HEDUSSIN® medicinal product will be used based on a recommendation from the doctor leading the treatment, after the product is purchased at a public pharmacy. The inclusion of the patient into the group where the given treatment method is used should not result from the study protocol. It should be dependent solely on the current medical practice and remain in accordance with the current medical knowledge.

Study drug

It is a preparation containing the dry extract of common ivy leaves as the active substance.

Excipients: non-crystallizing liquid sorbitol, potassium sorbate, xanthan gum, anhydrous citric acid, purified water

Pharmaceutical form: syrup

Potency: 100 ml of the syrup contains 825 mg of the dry extract of ivy leaves

Name and address of the manufacturer responsible for batch release: Phytopharm Kleka S.A.

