10.4.3. Adverse effects analysis

This Study is an efficacy assessment study (PAES) and its main aim is not focused on the research of the medicinal product safety – especially, the analysis of the reported adverse events will be conducted in a general manner as an auxiliary analysis in relation to the main aim of the Study, i.a. the efficacy assessment. The details on the safety of the used treatment contained within the Study Questionnaires will be included in the summaries of data on individual patients. Analysis and summary tables will be based on data from the study population taking into account the duration of exposure to the medicinal product under investigation.

All adverse effects will be coded in accordance with Medical Dictionary for Regulatory Activities (**MedDRA**).

The prevalence of all reported adverse effects and severe adverse effects occurring during the study will be presented in the form of tables.

In addition, summary tables will be presented, that will include data the maximum intensity of the adverse effect, the relationship to the study drug administration and related data on adverse effects as well as patients who discontinued treatment with the study drug due to the occurrence of adverse effects.

It is considered that related adverse effects occurring during the use of the study drug are any adverse effects that occur during an active study phase if:

They were not present prior to the first dose of study medication

or

• They were present prior to receiving the first dose of study drug, but its severity has been increasing during the observation.

All adverse effects occurring during the use of the study drug will be noted in the tables of adverse effects. Other medications used to treat concomitant diseases will be coded in accordance with the WHO Medication Coding Dictionary and will be summarized with the number and percentage of patients receiving concomitant medications and these patients will be grouped according to the pharmacological class of the medicine and International Non-proprietary Name (INN) of the drug.

10.5. Factors which may affect the statistical analysis and modify the results of the Study

- The Patients failure to report on the scheduled control visit
- The discontinuation of the study drug use for reasons other than adverse effects,
- Use other drugs during observation,

Study number: EUP/HED/008/2016

VERSION DATE: 21.11.2016

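### The efficacy set is defined by attendance alone, so a child who was enrolled but never took the syrup counts in the HEDUSSIN result

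*Protocol*

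**What the plan says.** Protocol section 10.2 bases the efficacy analysis on symptom change, wellbeing and duration of infection "in Patients who participated in all of the assessments outlined in the Study Protocol". The statistical methods entry of the protocol summary states the same rule: efficacy is analysed "on the basis of the population of Patients who will partake in all of the visits described in the Study Protocol". There are two visits.

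Section 10.1, immediately before, defines one class of patient. A Treated Patient is a "Patient who received at least one dose of study drug". Section 10.2 does not use the term.

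On timing, section 5.2 admits only children "who did not take the first dose of the syrup at the moment of the inclusion". Section 8.1 says the syrup is used on the doctor's recommendation, "after the product is purchased at a public pharmacy". Section 3.3, by contrast, describes the 500 as children who had begun HEDUSSIN in routine care.

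On exposure data, Table 1 in section 6.1 lists "The dose of the medicinal product used" at Visit 2, and section 12.2 asks in general terms for use of the drug to be recorded. Section 10.4.2 promises counts of children treated and of children who discontinued the drug. Section 10.4.3 promises adverse-effect tables that allow for length of exposure, and a table of children who stopped because of an adverse effect.

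**The concern.** Enrolment comes before intake by design, and intake then depends on a purchase outside the study. The efficacy rule does not ask whether intake took place. A child whose family never bought or gave the syrup, but who came back at 7 to 10 days, satisfies 10.2 as written, and that child's improvement is reported as the effect of HEDUSSIN.

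In a randomised trial there is a reason to keep such children, because dropping them can break the comparison between arms. Here there is one group, judged by change from Visit 1 to Visit 2, so no comparison needs protecting. The stated aim is the efficacy of this specific product, and section 1.3 says the data will serve marketing and training. A child who never took the product carries no information on that aim.

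The second part is about data. The planned tables need to know when the syrup was started, when it ended and why, and neither visit list names these items.

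**Working it through.** **1. Does any rule remove a never-taker?**

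| Place | What it requires | Removes a child with no dose who attends Visit 2? |
|---|---|---|
| 5.2 inclusion | No dose taken yet at Visit 1 | No; every child is in this state at entry |
| 5.3 exclusion | Age, hypersensitivity, certain prior drugs, respiratory neoplasm | No |
| 5.4 withdrawal | Leaving the study | No; this child stays |
| 10.1 Treated Patient | At least one dose | It would, but 10.2 does not refer to it |
| 10.2 and summary | Attendance | No |
| 3.3 | Describes children who started treatment | No; a description, not carried into 5.2 or 10.2 |

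The gap is real on the text. If the Table 1 dose item is completed, a never-taker can be identified at Visit 2, so the set can be corrected from planned data.

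**2. Are the promised exposure tables supplied?**

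- Number who discontinued treatment (10.4.2): needs stopping of the syrup, as distinct from leaving the study. Section 5.4 asks for a reason only in the second case.
- Duration of exposure (10.4.3): needs first-dose and last-dose dates. Neither is listed in Table 1 or 6.2.2. The Visit 1 date cannot stand in for the first dose, because enrolment and purchase both come before it.
- Stops due to adverse effects (10.4.3): needs a reason for stopping. None is listed for a child who stays in the study.
- The 10.4.3 rule for classing an adverse effect also turns on whether it was present before the first dose.

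**3. How large could the effect be?**

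Planned size: 50 physicians × 10 children = 500, which agrees with 10.3. (Section 5.1 also mentions 3000, a separate inconsistency not used here.)

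The protocol gives no rate of non-intake, so the following are assumptions. Let *f* be the fraction of 500 attenders who took no dose, and *r* their mean improvement relative to takers. Then

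reported mean change ÷ mean change in takers = (1 − *f*) + *f* × *r*.

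For example, *f* = 0.05 and *r* = 0.5 gives 0.95 + 0.025 = 0.975.

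| *f* | Never-takers | Left in the treated set | *r* = 0.5 | *r* = 1.0 | *r* = 1.2 |
|---|---|---|---|---|---|
| 2% | 10 | 490 | 0.990 | 1.000 | 1.004 |
| 5% | 25 | 475 | 0.975 | 1.000 | 1.010 |
| 10% | 50 | 450 | 0.950 | 1.000 | 1.020 |
| 20% | 100 | 400 | 0.900 | 1.000 | 1.040 |

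The result is understated if never-takers improve less than takers, unchanged if they improve equally, and overstated if they improve more (for instance, milder illness that made the syrup seem unnecessary).

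**The case against.** The case against is that this is a drafting slip. Section 3.3 speaks of children who started treatment, 6.2.1 describes the questionnaire as one for children using the product, and 10.1 sits directly above 10.2. Section 10.4.2 already plans separate counts of those treated and those who attended, so a difference would show. An analysis plan, which may exist, could add the one-dose condition from the Visit 2 dose item. Most of this is fair, and it limits the seriousness. It does not remove the point: the rule is stated twice in the protocol, without a dose condition, and should say what the authors apparently meant.

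Three stronger readings are tempting, and the document does not support them.

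- **That early stoppers also do not belong in the set.** Section 10.5 does list "The discontinuation of the study drug use for reasons other than adverse effects" among factors that may modify results. But analysing children whether or not they stopped is a legitimate treatment-policy choice. Section 1.1 puts a usual course at about 7 days and Visit 2 falls at 7 to 10 days, so having stopped by then is often just completion. Added antibiotics and other medicines are themselves assessed (2.1) and recorded at both visits, and their confounding affects every child.
- **That the bias exceeds sampling error.** With an assumed 50% recovered, the half-width is 1.96 × √(0.5 × 0.5 / 500) = 4.4 points. Counting 25 children, all recovered, as failures moves 50% to 45%. If half of them had recovered, it moves only to 47.5%. The protocol plans no proportion recovered, and recoding stoppers as failures is itself debatable.
- **That stop dates and reasons will be lost.** The questionnaire is not shown, and 12.2 asks for drug use. All that can be said is that Table 1 and 6.2.2 do not list these items.

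**Conclusion.** The point holds for children who never take the syrup. Sections 10.2 and the summary count them in the efficacy result, at odds with 3.3 and without use of the definition in 10.1. It also holds that 10.4.2 and 10.4.3 promise exposure and discontinuation tables for which the visit lists name no start date, stop date or reason. It does not extend to removing early stoppers.

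The size and direction cannot be derived from the document. Under assumed non-intake of 2% to 20% and relative improvement of 0.5 to 1.2, the reported mean change is 0.90 to 1.04 times that in takers. If few children never start, as seems likely among those for whom the syrup has just been recommended, the effect is small. The case for the change rests on its being specific and nearly free, and on the absence of any benefit from keeping untreated children in an uncontrolled series.

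**What to change.** In 10.2 and the summary, replace the attendance rule with:

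*Efficacy is analysed in Treated Patients (10.1) who attended both visits; children who attended both but took no dose are listed separately.*

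Early stoppers remain in this set.

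Add three items to Visit 2 in Table 1 and 6.2.2:

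- date of first dose;
- date of last dose;
- reason the syrup ended: still taking / course completed / recovered / adverse effect / no effect / other.

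These supply the tables already promised in 10.4.2 and 10.4.3, and let a reader distinguish a completed course from a stop for no effect.

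The cost is one sentence in two places, three questionnaire fields and a slightly smaller efficacy set. No visit or procedure is added, so the non-interventional status is untouched.
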